7.2.4. Visit and Assessment Changes Due to COVID-19

The investigator may opt to have the participant attend an unscheduled visit, if deemed necessary, at any time during the study. Some clinic visits may be shortened and/or conducted remotely, if required due to the COVID-19 (or other) pandemic, and with approval from the Sponsor's Medical Monitor. Protocol waivers or exemptions are not allowed.

Changes in scheduled visits and corresponding assessments due to COVID-19 (or other) pandemic restrictions will be reported. Submission datasets will include flags for all missing visits and assessments where the “not done” field is indicated and the reason for “not done” contains “COVID” in the description field. The protocol deviation log will also be reviewed to assess whether deviations are due to COVID-19.

7.2.5. Missing and Partial Data

Missing or partially missing concomitant medications and AEs start and stop dates will be imputed as described in [Appendix 2](#). However, imputed dates will not be presented in the listings as their sole purpose will be for the classification of the medications and the AEs.

Missing data will be handled as described in the following sections:

- Missing safety data will not be imputed except for AEs and concomitant medication start and stop dates as described above.
- For multi-item questionnaires such as CAPS-5, we expect few missing items in the total score such as the CAPS-5 total score. The electronic clinical outcome assessment platform adopted for this study prevents the rater from proceeding to the next item if there are missing items in the questionnaire.
- Missing data for the primary estimand and key secondary estimands will not be explicitly imputed for main analyses but will be imputed in sensitivity analyses.
- Missing data will not be imputed for other secondary endpoints, and exploratory endpoints.

7.3. Hypotheses Testing

To evaluate the efficacy of JZP150 at doses of 4 mg/day and 0.3 mg/day compared with placebo, pairwise comparisons between each of the doses and placebo will be conducted at the end of Week 12 for the primary and key secondary endpoints, resulting in up to six separate null hypotheses to be tested.

The null (H_{0i}) and alternative (H_{Ai}) hypotheses for analysis of the primary efficacy and key secondary efficacy variables (CAPS-5, CGI-S and PGI-S) at each of JZP150 4 mg and 0.3 mg vs placebo are:

$H_{01}(\text{CAPS-5})$: $\Delta\mu(\text{JZP150, 4 mg}) = \Delta\mu(\text{Placebo})$ vs $H_{A1}(\text{CAPS-5})$: $\Delta\mu(\text{JZP150, 4 mg}) \neq \Delta\mu(\text{Placebo})$

$H_{02}(\text{CGI-S})$: $\Delta\mu(\text{JZP150, 4 mg}) = \Delta\mu(\text{Placebo})$ vs. $H_{A2}(\text{CGI-S})$: $\Delta\mu(\text{JZP150, 4 mg}) \neq \Delta\mu(\text{Placebo})$

$H_{03}(\text{PGI-S})$: $\Delta\mu(\text{JZP150, 4 mg}) = \Delta\mu(\text{Placebo})$ vs $H_{A3}(\text{PGI-S})$: $\Delta\mu(\text{JZP150, 4 mg}) \neq \Delta\mu(\text{Placebo})$

Jazz Pharmaceuticals
 {Statistical Analysis Plan - Protocol #}JZP150-201-02

H₀₄(CAPS-5): $\Delta\mu_{(JZP150, 0.3 \text{ mg})} = \Delta\mu_{(\text{Placebo})}$ vs H_{A4}(CAPS-5): $\Delta\mu_{(JZP150, 0.3 \text{ mg})} \neq \Delta\mu_{(\text{Placebo})}$
 H₀₅(CGI-S): $\Delta\mu_{(JZP150, 0.3 \text{ mg})} = \Delta\mu_{(\text{Placebo})}$ vs H_{A5}(CGI-S): $\Delta\mu_{(JZP150, 0.3 \text{ mg})} \neq \Delta\mu_{(\text{Placebo})}$
 H₀₆(PGI-S): $\Delta\mu_{(JZP150, 0.3 \text{ mg})} = \Delta\mu_{(\text{Placebo})}$ vs H_{A6}(PGI-S): $\Delta\mu_{(JZP150, 0.3 \text{ mg})} \neq \Delta\mu_{(\text{Placebo})}$

where $\Delta\mu$ represents mean change from baseline to end of Week 12 in the CAPS-5 total score, CGI-S or PGI-S.

Specifically, for the primary endpoint, the null hypothesis states that there is no difference in the mean change in the CAPS-5 total score from Baseline to Week 12 between the indicated JZP150 dose level and placebo arm. The alternative hypothesis states that the mean change in the CAPS-5 total score is not equal between the indicated JZP150 dose level and placebo.

The null and alternative hypotheses for each of the key secondary estimand variables (CGI-S and PGI-S) are defined similarly as for the primary efficacy estimand variable.

7.4. Level of Significance & Multiplicity Adjustment

A fixed sequence hierarchical testing strategy will be implemented for the primary and key secondary endpoints (as illustrated in [Table 4](#)) to preserve the family-wise Type 1 error rate at the significance level of 0.05. Testing will begin with the comparison of JZP150 4 mg vs placebo for the primary efficacy endpoint followed by sequential testing of the key secondary efficacy endpoints in the order of CGI-S and then PGI-S. If all three null hypotheses are rejected, then similar hierarchical sequential testing of the endpoints will be performed for comparing JZP150 0.3 mg vs placebo. The testing will stop when the p-value exceeds the significance level of 0.05. All tests will be conducted at a 2-sided significance level of 0.05. Multiplicity adjustment will not be conducted for other secondary efficacy endpoints or for the exploratory endpoints.

Statistical hypotheses to be tested (in sequential order):

1. Change in the primary estimand variable (the CAPS-5 total score) from Baseline to Week 12, JZP150 4 mg vs placebo
2. Change in the key secondary estimand variable (CGI-S) from Baseline to Week 12, JZP150 4 mg vs placebo
3. Change in the key secondary estimand variable (PGI-S) from Baseline to Week 12, JZP150 4 mg vs placebo
4. Change in the primary estimand variable (the CAPS-5 total score) from Baseline to Week 12, JZP150 0.3 mg vs placebo
5. Change in the key secondary estimand variable (CGI-S) from Baseline to Week 12, JZP150 0.3 mg vs placebo
6. Change in the key secondary estimand variable (PGI-S) from Baseline to Week 12, JZP150 0.3 mg vs placebo

Jazz Pharmaceuticals
 {Statistical Analysis Plan - Protocol #}JZP150-201-02

Table 4: Fixed Sequence Testing Strategy

Sequence	Variable	JZP150 Dose	Null Hypothesis	Expected Effect Size	Power
1	CAPS-5	4 mg	$H_{01}(\text{CAPS-5})$	0.57	93.4%
2	CGI-S	4 mg	$H_{02}(\text{CGI-S})$	0.50	86%
3	PGI-S	4 mg	$H_{03}(\text{PGI-S})$	0.50	86%
4	CAPS-5	0.3 mg	$H_{04}(\text{CAPS-5})$	0.57	80.9%
5	CGI-S	0.3 mg	$H_{05}(\text{CGI-S})$	0.50	70%
6	PGI-S	0.3 mg	$H_{06}(\text{PGI-S})$	0.50	70%

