4.2. Scientific Rationale for Study Design

A 12-week, placebo-controlled, parallel-group, fixed-dose design of placebo and 2 doses of JZP150 was selected for the following reasons: 1) data obtained from this study design will inform the development, design, and dose selection for a phase 3 trial; 2) this study design has the potential to identify a no-effect or minimally effective dose and will characterize the efficacy and safety at the highest dose intended for clinical use and inform exposure-response; 3) this study and choice of control is in accordance with ICH E6(R2) and E10 guidelines; 4) the use of only 2 active treatment arms is expected to minimize placebo-related expectancy effects; 5) the 12-week double-blind treatment duration was chosen to maximize active-placebo differences.

The scientific rationale for key study design elements is provided below.

Stratification Elements

Randomization will be stratified by the presence or absence of concomitant use of SSRIs/SNRIs. Many PTSD patients are being treated with SSRI/SNRI medications and this enrollment strategy

is therefore reflective of the real-world patient populations. This enrollment strategy will permit assessment of safety and efficacy in both users and non-users of these antidepressants.

Posttraumatic stress disorder diagnosis and severity of condition

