In single dose administration of 0.3 mg, JZP150 plasma levels were not above 1 ng/mL during most of the 24 hour period post dose; however, multiple dose administration of 0.5 mg QD resulted in mean plasma concentration levels in the 1 to 2 ng/mL range. Thus, based on these data and the observed between-subject variability, the 0.3 mg dose administered QD is not expected to maintain JZP150 plasma concentrations consistently above the threshold of 1 ng/mL to sustain the AEA levels at the target concentration above 2 to 2.5 ng/mL in most study participants. Therefore, the 0.3 mg dose should provide a means to identify a no-effect or minimally effective dose. Additionally, PTSD patients may have increased activity of FAAH and reduced levels of baseline AEA, and therefore may require higher AEA elevations compared with healthy volunteers. The 0.3 mg dose will also provide a low end of a broad range of concentrations to explore exposure-response.

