9.2. Sample Size Determination

Approximately 270 participants will be randomized (2:1:2) to receive placebo, 0.3 mg JZP150, or 4 mg JZP150. Participants will be stratified by the presence or absence of concomitant use of SSRIs/SNRIs.

The sample size was determined based on ensuring at least 80% marginal power to detect a difference of 6 between placebo and each dose of JZP150 for the mean change in CAPS-5 total symptom severity score from Baseline to Week 12. The sample sizes for the estimated 70% of subjects completing the 12-week dosing period for each arm (placebo [n = 75], 0.3 mg JZP150 [n = 38], and 4 mg JZP150 [n = 75]) provides a marginal power of 80.9% and 93.4% for comparing the low dose vs placebo and high dose vs placebo, respectively. Calculations are based on assuming a common standard deviation of 10.5, using a two-sample t-test, and two-sided significance level of 0.05. To account for a 30% dropout, the sample size will be 270 participants to ensure that a minimum of 188 participants have 12 weeks of treatment data.

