9.4.1.1. Multiplicity Adjustments

A fixed sequence hierarchical testing strategy will be implemented for the primary and key secondary endpoints (as illustrated in [Table 5](#)) to preserve the family-wise Type 1 error rate at the significance level of 0.05. Testing will begin with the comparison of the JZP150 4 mg dose vs Placebo for the primary efficacy variable followed by sequential testing of the key secondary efficacy variables in the order of CGI-S and then PGI-S. If all three null hypotheses are rejected,

then similar hierarchical sequential testing of the endpoints will be performed for comparing JZP150 0.3 mg dose vs placebo. The testing will stop when the p-value exceeds the significance level of 0.05. All tests will be conducted at a 2-sided significance level of 0.05.

Table 5: Hierarchical Testing Strategy

Gatekeeper Family	Endpoint	Null Hypothesis	Effect Size	Power
1	CAPS-5	$H_1: JZP150 4 \text{ mg} = \text{Placebo}$	0.57	93.4%
2	CGI-S	$H_2: JZP150 4 \text{ mg} = \text{Placebo}$	0.50	86%
3	PGI-S	$H_3: JZP150 4 \text{ mg} = \text{Placebo}$	0.50	86%
4	CAPS-5	$H_4: JZP150 0.3 \text{ mg} = \text{Placebo}$	0.57	80.9%
5	CGI-S	$H_5: JZP150 0.3 \text{ mg} = \text{Placebo}$	0.50	70%
6	PGI-S	$H_6: JZP150 0.3 \text{ mg} = \text{Placebo}$	0.50	70%

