5.3. Power and Sample Size Calculations

Approximately 270 participants will be randomized (2:1:2) to receive placebo, 0.3 mg JZP150, or 4 mg JZP150.

The sample size was determined based on ensuring at least 80% marginal power to detect a difference of 6 between placebo and each dose of JZP150 for the change in CAPS-5 total score from Baseline to Week 12 ([Stefanovics et al 2018](#); [Stein et al 2006](#)). The sample size for the estimated 70% of evaluable participants completing the 12-week dosing period for each arm (placebo [$n = 75$], 0.3 mg JZP150 [$n = 38$], and 4 mg JZP150 [$n = 75$]) provides a marginal power of 93.4% and 80.9% for comparing the high dose vs placebo and low dose vs placebo, respectively. Calculations are based on assuming a common standard deviation of 10.5, using a two-sample t-test, and two-sided significance level of 0.05. To account for a 30% dropout, a total of 270 participants will be randomized to ensure that a minimum of 188 participants have 12 weeks of intervention data.

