The model will include CGI-S or PGI-S change from Baseline to Week 12 as the dependent variable; randomized treatment group, week (as a discrete factor), treatment group by week interaction, randomization stratum, stratum by week interaction, the CGI-S or PGI-S score at Baseline, and baseline by week interaction, as fixed effects, and week as a repeated effect. An unstructured variance-covariance matrix will be used to model the correlation among repeated measurements. Missing data will not be explicitly imputed and will be handled with the MMRM modeling. Alternative covariance structures will be similar to the methodology specified in [Section 9.1.2](#). Similar summary statistics described in [Section 9.1.2](#) will be provided. Similar SAS codes provided in [Section 9.1.2](#) will be used.

A box plot will be presented for the change in CGI-S and PGI-S from Baseline to end to Week 12 by randomized treatment group, separately. The CGI-S and PGI-S data will also be summarized by time point separately.

A separate SAP will be provided for the anchor-based global assessment to determine CAPS-5's clinically meaningful within-patient change threshold, using CGI-S and PGI-S as anchor scales. This supplemental SAP will present analyses intending to support the analysis of the CGI-S and PGI-S assessment as continuous variables.

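### Does the Power column in SAP Table 4 and Protocol Table 5 need to change because it ignores the fixed testing sequence?

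*SAP*

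**What the plan says.** SAP Section 7.4 sets a six-step fixed sequence at two-sided 0.05: CAPS-5, CGI-S and PGI-S for 4 mg against placebo, then the same three for 0.3 mg. The step between doses reads "If all three null hypotheses are rejected, then similar hierarchical sequential testing of the endpoints will be performed for comparing JZP150 0.3 mg vs placebo", and testing ends at the first p-value above 0.05. Protocol Section 9.4.1.1 has the same rule ("then similar hierarchical sequential testing of the endpoints will be performed for comparing JZP150 0.3 mg dose vs placebo").

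SAP Table 4 and Protocol Table 5 give one power figure per step: 93.4, 86, 86, 80.9, 70 and 70%. The effect sizes beside them are 0.57 (CAPS-5) and 0.50 (CGI-S, PGI-S), identical for both doses. The SAP heads that column *Expected Effect Size*; the protocol says only *Effect Size*.

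The sample-size text names the quantity. Protocol Section 9.2 states "The sample size was determined based on ensuring at least 80% marginal power to detect a difference of 6" for each dose against placebo, and SAP Section 5.3 says the planned numbers give what it "provides a marginal power of 93.4% and 80.9% for comparing the high dose vs placebo and low dose vs placebo, respectively".

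On the role of the low dose, Protocol Section 4.2 says "this study design has the potential to identify a no-effect or minimally effective dose". Section 4.3 says "the 0.3 mg dose administered QD is not expected to maintain JZP150 plasma concentrations consistently above the threshold of 1 ng/mL" and concludes "Therefore, the 0.3 mg dose should provide a means to identify a no-effect or minimally effective dose".

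**The concern.** A power column in a table whose rows are numbered in test order is easily read as power under that order. It is not. Step 4 is tested only if steps 1 to 3 all reject, and step 6 only if steps 1 to 5 all reject, yet no power under the sequence appears in either document. The word marginal is attached to the two CAPS-5 figures in the sample-size text but not to the tables, and never to the CGI-S and PGI-S figures.

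The heading *Expected Effect Size* also sits awkwardly at 0.3 mg, a dose that Protocol Section 4.3 describes as a possible no-effect or minimally effective dose.

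At stake would be how the low dose is read. The trial is meant to inform dose selection for phase 3. Someone relying on the table alone would put the chance of missing a true 6-point CAPS-5 effect at 0.3 mg at 100 − 80.9 = 19.1%, when the chance of no formal rejection is larger. That reader might then take an unrejected or untested 0.3 mg comparison as evidence of no effect.

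**Working it through.** **Inputs.** From SAP 5.3 and Protocol 9.2: completers 75 (placebo), 38 (0.3 mg), 75 (4 mg); SD 10.5; CAPS-5 difference 6; two-sample t-test; two-sided 0.05. From the two tables: effect size 0.50 for CGI-S and PGI-S. The correlation among the three endpoints is not in the documents; a common value of 0 to 0.9 is assumed. SAP 9.2.2 plans a threshold analysis for CAPS-5 "using CGI-S and PGI-S as anchor scales", which suggests the scales are related but gives no value.

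**1. Reproduce the tabulated figures, each test alone.** Noncentrality = d / √(1/n₁ + 1/n₂), with d = 6/10.5 = 0.571 for CAPS-5.

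| Comparison | Noncentrality | df | Power | Tables |
|---|---|---|---|---|
| CAPS-5, 4 mg (75 v 75) | 0.571/0.1633 = 3.50 | 148 | 93.5% | 93.4% |
| CGI-S or PGI-S, 4 mg | 0.50/0.1633 = 3.06 | 148 | 86.0% | 86% |
| CAPS-5, 0.3 mg (38 v 75) | 0.571/0.1991 = 2.87 | 111 | 81.2% | 80.9% |
| CGI-S or PGI-S, 0.3 mg | 0.50/0.1991 = 2.51 | 111 | 70.2% | 70% |

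With d rounded to 0.57, the CAPS-5 figures are 93.4% and 81.0%. All six entries are therefore correct single-test powers.

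**2. Power under the sequence.** Power at step k is the probability that steps 1 to k all reject. If all six tests were independent, the stated powers would simply multiply: 0.934; × 0.86 = 0.803; × 0.86 = 0.691; × 0.809 = 0.559; × 0.70 = 0.391; × 0.70 = 0.274.

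The tests are not independent. The shared placebo arm gives a between-dose correlation of (1/75) / √[(1/75 + 1/75)(1/75 + 1/38)] = 0.41. A simulation of 1,000,000 draws of six correlated normal test statistics, each with its single-test power matched to part 1, gave:

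| Step | Tables | ρ = 0 | ρ = 0.5 | ρ = 0.7 | ρ = 0.9 |
|---|---|---|---|---|---|
| 1 CAPS-5, 4 mg | 93.4 | 93.6 | 93.6 | 93.5 | 93.6 |
| 2 CGI-S, 4 mg | 86 | 80.5 | 82.5 | 83.8 | 85.4 |
| 3 PGI-S, 4 mg | 86 | 69.2 | 75.0 | 78.0 | 81.9 |
| 4 CAPS-5, 0.3 mg | 80.9 | 57.5 | 63.4 | 66.2 | 69.6 |
| 5 CGI-S, 0.3 mg | 70 | 42.8 | 51.0 | 55.0 | 60.1 |
| 6 PGI-S, 0.3 mg | 70 | 31.8 | 43.4 | 48.9 | 56.1 |

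At ρ = 0.5 to 0.9, step 4 is not reached in 100 − 75.0 = 25.0% down to 100 − 81.9 = 18.1% of trials, and is not rejected in 100 − 63.4 = 36.6% down to 100 − 69.6 = 30.4%.

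**3. A smaller low-dose effect.** If 0.3 mg had half the tabulated effect (an assumption), step 4 power would be 29.6% alone and 21.5–27.3% in sequence over ρ = 0 to 0.9.

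**4. What is reported if the gate closes.** SAP 9.1.2 provides the Week 12 LS mean difference, standard error, 95% CI and p-value for active treatment against placebo, with no condition tied to the sequence. The approximate half-width for 0.3 mg is t(111) × 10.5 × √(1/75 + 1/38) = 1.98 × 10.5 × 0.199 = 4.1 points.

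**The case for a change.** The best case for a change is that the loss is real and does not hinge on the assumed correlation. At every value tried, step 4 falls below 80%, the figure both sample-size sections set for each dose. Four of the six rows are never called marginal anywhere. The remedy looks cheap: a label, a second column, a reworded heading and a sentence on how to read a failed gate. The SAP already gives a comparable caution about power in subgroups (Section 7.5).

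The arithmetic stands, and so does the missing label. The rest does not carry a change:

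- The 80% target is stated as marginal power, and at 81% the design meets it. The two figures called marginal in SAP 5.3 are the same ones printed in Table 4, and the gate and stopping rule appear in the same section as that table. A statistician reads the other four the same way, and part 1 of the working confirms it.
- A sequential column would rest on a correlation the documents do not supply, and its entries at step 6 would run from 32 to 56% depending on that choice.
- The 6-point difference is set as the difference to detect for each dose, which is a legitimate sizing assumption. Protocol 4.3 concerns plasma drug and anandamide levels and states no expected CAPS-5 effect. Only the word *Expected* in one heading is loose.
- Neither document says that failing or not reaching step 4 establishes a no-effect dose. The protocol speaks of potential and of a means to identify one. A closed gate removes the formal claim but not the low-dose estimate and its interval, and an exposure-response analysis may be reported separately.

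**Conclusion.** No change follows. This is a gap in labelling that a reader fills from the sample-size section. The tabulated powers are correct for what the plan says they are, to within 0.3 points. Power under the sequence is lower at every step after the first: by about 1 to 6 points at step 2, 11 to 23 at step 4 and 14 to 38 at step 6, against the printed figures. Those ranges assume the plan's own effect sizes, full planned completer numbers and a common between-endpoint correlation of 0 to 0.9.

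None of this alters the sample size, the order of tests, control of the family-wise error rate, the models or the reported intervals. The SAP is dated 12 December 2023 and already describes misconduct at one site and limited follow-up after intercurrent events, so an added planning figure at that stage could not affect the design. Editing the protocol table would also require an amendment with ethics approval (Protocol 10.1.1). Calling the column marginal would be harmless, but no analysis or conclusion depends on it.

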7.5. Subgroups and Subgroup Analyses

Subgroup analyses will be conducted on the primary and key secondary efficacy endpoints for the following:

- Randomization stratum: presence vs absence of concomitant use of SSRIs/SNRIs
- Age group 1 (years): ≤ 65 vs > 65
- Age group 2 (years): ≤ 45 vs > 45
- Gender (male vs female)
- Race (white vs black vs other)
- Ethnicity (Hispanic or Latino vs Not Hispanic or Latino)
- High enrolling sites (≥ 20 randomized participants) (high enrolling sites combined vs all other sites combined)

Should there be less than 20 participants in any subgroup, then only summary statistics will be presented.

The output for estimating the treatment difference within subgroup will not be provided (least square [LS] means, standard error [SE], LS Mean Difference (95% confidence interval [CI]) or median difference (95% CI) and p-value) if the data are too sparse.

It should be noted that the study was not designed to detect treatment differences with high statistical power within any subgroups.

7.6. Intercurrent Event Strategies

The main ICE of treatment discontinuation will be handled using two different strategies as defined below:

The treatment policy (based on the Intention to Treat (ITT) principle, where value of the variable of interest is used regardless of whether the ICE occurs) will be used as the

Jazz Pharmaceuticals
 {Statistical Analysis Plan - Protocol #}JZP150-201-02

primary strategy to address the ICE of treatment discontinuation in the main analyses for the primary and key secondary estimands. It is defined as the pharmacologic effect of JZP150 compared to placebo over the protocol-specified treatment period (i.e., 12 weeks), regardless of whether randomized treatment is continued. Analyses will be conducted using all data collected through Week 12 regardless of treatment discontinuation. Efficacy data collected after treatment discontinuation will be included in the main analyses.

The hypothetical approach (assuming treatment discontinuation did not occur) will be used as the alternative strategy to address the ICE of treatment discontinuation in the repeated analyses for the primary and key secondary estimands. It is defined as the pharmacologic effect of JZP150 compared to placebo assuming continuation of randomized treatment for the protocol-specified treatment period (i.e., 12 weeks). Analyses will be conducted using only data collected at time points that are at or prior to treatment discontinuation. Efficacy data collected after treatment discontinuation will be discarded for the alternative strategy.

Other possible ICEs include study intervention non-compliance, significant protocol deviations, new trauma, or initiation or adjustment of concomitant medications for PTSD, which are not permitted per protocol, but nevertheless can still occur. It is anticipated that the occurrence of these events will be rare; therefore, both primary and key secondary estimands use the treatment policy approach to address these other ICEs.

For all secondary efficacy endpoints, unless specified otherwise, all ICEs will be addressed by the treatment policy strategy.

